V1.4	05DEC2017	Rationale for moving from V1.4 to V1.5: due to an unexpected investigational medicinal product (IMP) quality event, without safety concerns, the use of dose 2 IMP is discontinued from the pivotal phase III study CLN-PXT3003-02 upon Sponsor decision (September 18 th , 2017). The stability testing at Quay Pharma (UK) observed the occurrence of crystals in one stability batch of PXT3003 dose 2 at month 18 (September 14 th , 2017), whereas this was not the case at month 12. This new finding is inconsistent with the dose 2 IMP release criteria and therefore does not meet the ICH Harmonized Tripartite Guideline for Stability Testing of New Drug Substances and Products. Hence, the patient arm of PXT3003 dose 2 will early terminate the study. They will be offered to enter the extension study CLN-PXT3003-03 to receive the equivalent of dose 2 (5 mL per administration), by using of its equivalent dose, i.e. twice the dose 1 IMP (2x5 mL, i.e. 10 mL) per administration. Furthermore, all patients using dose 1 IMP or placebo will continue to receive dose 1 IMP or placebo (5 mL per administration) in the pivotal phase III study CLN-PXT3003-02 as planned.

IMPACTED OF THE PROTOCOL AMENDMENT V1.4

1. How to manage the dose 2 patient group discontinuation?	
The PXT3003 dose 2 study arm will discontinue prematurely from study CLN-PXT3003-02, in accordance with section 11.6.1 "if the study is prematurely discontinued then enrolled patients should be called for an end of study visit".
 
Hence, there is no need to implement additional information in the protocol.
 
The sites will receive additional useful instructions to organise the recall of dose 2 IMP patients.

2 Statistical sections: how to manage incomplete data	
Due to incomplete data in the dose 2 arm, the missing data will be evaluated as described in the section 14.5 of the protocol.

3 Section 11.7 follow up extension study – adapted as followed	
Patients who completed this 15-month study or who were prematurely discontinued from the PXT3003 dose 2 administration will be offered to enter the open-label extension study CLN-PXT3003-03.
 
Patients previously assigned to dose 2 PXT3003 will receive the equivalent of dose 2 (i.e. 5 mL per administration), by use of its equivalent dose, i.e. twice the dose 1 PXT3003 (2x5 mL, i.e. 10 mL per administration) in the study CLN-PXT3003-03.
 
Patients previously assigned to dose 1 PXT3003 or placebo and who have completed the pivotal phase III study will receive dose 1 PXT3003 (5 mL) in the study CLN-PXT3003-03.
 
Hence the protocol of extension study has been amended to assign all placebo patients to dose 1 IMP only, whereas patients previously assigned to dose 1 IMP will continue to do so. As a consequence of the difference of IMP volume (i.e. 5 mL and 10 mL) to be administered the study has become an open-label study that no longer randomizes patients to study treatment.

Signature page for sponsor representative**PROTOCOL CLN-PXT3003-02****STUDY PLEO-CMT (PLEO-CHARCOTMARIETOOTH)**

**International, multi-center, randomized, double-blind, placebo-controlled phase III study assessing
in parallel groups the efficacy and safety of 2 doses of PXT3003
in patients with Charcot-Marie-Tooth Disease type 1A treated 15 months**

EUDRACT N° 2015-002378-19**IND N° 122505****Protocol version: N° 1.4 dated December 05th 2017**

The study will be conducted in compliance with the following protocol and will be carried out in accordance with Good Clinical Practice (GCP) as required by the ICH GCP E6 and local applicable regulatory requirements in the participating countries.

Rationale for moving from V1.3 to V1.4: due to an unexpected investigational medicinal product (IMP) quality event, without safety concerns, the use of dose 2 IMP is discontinued from the pivotal phase III study CLN-PXT3003-02 upon Sponsor decision (September 18th, 2017).

The stability testing at Quay Pharma (UK) observed the occurrence of crystals in one stability batch of PXT3003 dose 2 at month 18 (September 14th, 2017), whereas this was not the case at month 12. This new finding is inconsistent with the dose 2 IMP release criteria and therefore does not meet the ICH Harmonized Tripartite Guideline for Stability Testing of New Drug Substances and Products.

Hence, the use of PXT3003 dose 2 will be prematurely discontinued from the study. Patients assigned to PXT3003 dose 2 will therefore be withdrawn from study CLN-PXT3003-02 upon completion of the end-of-study assessments and will be offered to enter the extension study CLN-PXT3003-03 to receive the equivalent of dose 2 IMP (5 mL per administration), by use twice the dose 1 IMP (2x5 mL, i.e. 10 mL) per administration.

Furthermore, all patients using dose 1 IMP or placebo will continue to receive dose 1 IMP or placebo (5 mL per administration) in the pivotal phase III study CLN-PXT3003-02 as planned.

I fully agree to the contents of this protocol which gives all the necessary information to conduct this study. I hereby accept to coordinate this study:

The site investigator Date :

Name:

Hospital: Signature:

Address:

Summary of Changes

From V1.3 to V1.4

Nº Changes Page / section	V1.3 (Initial text)	V1.4 (Text modified)
Each page (heading)	Protocol CLN-PXT3003-02, Version 1.3	Protocol CLN-PXT3003-02, Version 1.4
Pages: 1-4-5-6	
Protocol version: N° 1.3 and rationale moving from V1.3 to V1.4
	
Protocol version N°1.4
 
Rationale for moving from V1.3 to V1.4: due to an unexpected investigational medicinal product (IMP) quality event, without safety concerns, the use of dose 2 IMP is discontinued from the pivotal phase III study CLN-PXT3003-02 upon Sponsor decision (September 18th, 2017).
 
The stability testing at Quay Pharma (UK) observed the occurrence of crystals in one stability batch of PXT3003 dose 2 at month 18 (September 14th, 2017), whereas this was not the case at month 12. This new finding is inconsistent with the dose 2 IMP release criteria and therefore does not meet the ICH Harmonized Tripartite Guideline for Stability Testing of New Drug Substances and Products.
 
Hence, the patient arm of PXT3003 dose 2 will early terminate the study. They will be offered to enter the extension study CLN-PXT3003-03 to receive the equivalent of dose 2 (5 mL per administration), by using of its equivalent dose, i.e. twice the dose 1 IMP (2x5 mL, i.e. 10 mL) per administration.
 
Furthermore, all patients using dose 1 IMP or placebo will continue to receive dose 1 IMP or placebo (5 mL per administration) in the pivotal phase III study CLN-PXT3003-02 as planned.

Synopsis Planned dates	NA	
Last patient out (ie., end of study): expected Q12018 in all the countries, except in Germany where the LPO is expected Q3 2018*
 
Clinical Study Report: expected Q2 2019,
 
* due to longer interruption of the study in Germany regarding the occurrence of crystals in the dose 2 IMP, the LPO in Germany is expected in Q3 2018

Section 11.2.7 Bullet 8	Blood samples for PK (one before dosing, and one 90 minutes after drug intake)	Blood samples for PK (one before dosing, and one 90 minutes after drug intake) 
 ○ Attention: PK samples are not applicable in the dose 2 arm if the end of study visit is performed due to discontinuation of the dose 2 arm
Section 11.7 Follow up extension study	NA	
From V1.4:
 
Patients who completed this 15-month study or who were prematurely discontinued from the PXT3003 dose 2 administration will be offered to enter the open-label extension study CLN-PXT3003-03.
 
Patients previously assigned to dose 2 PXT3003 will receive the equivalent of dose 2 (i.e. 5 mL per administration), by use of its equivalent dose, i.e. twice the dose 1 PXT3003 (2x5 mL, i.e. 10 mL per administration) in the study CLN-PXT3003-03.
 
Patients previously assigned to dose 1 PXT3003 or placebo and who have completed the pivotal phase III study will receive dose 1 PXT3003 (5 mL) in the study CLN-PXT3003-03.
 
Hence the protocol of extension study has been amended to assign all placebo patients to dose 1 IMP only, whereas patients previously assigned to dose 1 IMP will continue to do so. As a consequence of the difference of IMP volume (i.e. 5 mL and 10 mL) to be administered the study has become an open-label study that no longer randomizes patients to study treatment.

1. SYNOPSIS

Study No:	CLN-PXT3003-02	Study name:	PLEO-CMT
Title	International, multi-center, randomized, double-blind, placebo-controlled phase III study assessing in parallel groups the efficacy and safety of 2 doses of PXT3003 in patients with Charcot-Marie-Tooth disease type 1A treated for 15 months.		
Phase	Phase III		
Indication	Charcot Marie Tooth Disease - Type 1A (CMT1A)		
Investigational Drug	PXT3003, a fixed dose combination of RS-Baclofen, Naltrexone hydrochloride and D-Sorbitol		
Study Design	Double-blind, randomized, placebo-controlled, 3 parallel groups, international multi-center study for 15 months (65 weeks).		
Study duration	Patients will be randomized after a screening period (up to 30 days) during which selection criteria are verified and baseline assessments such as electrophysiological testing, lab tests and ECG are performed. Then, after randomization, patients will be included in the study under double blind study medication for 15 months.		
Total expected number of patients	A total of at least 300 patients will be randomized (1:1:1) into 3 parallel groups: PXT3003 Dose 1, PXT3003 Dose 2 or matching Placebo (100/group), to achieve a power of at least 90% to detect the expected effect as significant with the primary efficacy analysis.		
Rational	
CMT1A, the most frequent CMT subtype (40 to 50% of all CMT), belongs to the group of inherited, progressive, chronic sensory and motor peripheral neuropathies referred to as Charcot-Marie-Tooth (CMT) disease or also as "Hereditary Motor and Sensory Neuropathy" (HMSN) or "Peroneal Muscular Atrophy" (PMA).
 
CMT1A is caused by a specific duplication in the gene encoding for the "peripheral myelin protein of 22 Kilodalton" (PMP22) expressed in Schwann cells and could be defined as a gene-dosage disease causing a 1.5-fold over-expression of the PMP22 protein in Schwann cells. The moderately elevated expression of this gene disrupts peripheral nerve myelination by Schwann cells and consecutively, slows signal transmission alongside the axons and deprives them of important neurotrophic factors normally provided by mature Schwann cells. Ultimately, axonal loss is responsible for the clinical phenotype due to muscle and sensory organ denervation.
 
PXT3003, is a fixed dose combination of (RS)-baclofen, naltrexone hydrochloride and D-sorbitol selected via a Systems Biology approach and developed by Pharnext, with the aim to lower toxic PMP22 gene over-expression in CMT1A.
 
The expected effect of the combination of the three drugs in the treatment of CMT1A has been demonstrated first pre-clinically ex vivo and in vivo (Chumakov, Milet et al., 2014), and then by a phase II proof of concept study testing 3 doses of the combination at the same ratio compared to Placebo in 80 patients with CMT1A treated for 12 months. This phase II study demonstrated the good tolerability and safety of 3 tested doses of PXT3003 (primary outcome measure) and provided preliminary evidence of efficacy with a significant 'dose-effect' and an increasing effect among the 3 tested doses demonstrating positive results after 12 months on the selected relevant clinical and electrophysiological outcome measures only for the highest Dose. At this highest dose baclofen, naltrexone and sorbitol were administrated at much lower doses (10 to 100 times less) than used for their respective approved indications as daily doses were 6 mg baclofen, 0.7 mg naltrexone and
		

Rational (con't)	
210 mg sorbitol (Attarian, Vallat et al., 2014).
 
It is postulated that PXT3003 deserves further clinical investigation in a pivotal confirmatory study in a larger CMT1A population. For this next study, 2 doses will be tested, compared to placebo: the highest dose found effective in the phase II and a higher dose (double dose with the same ratio between each active components of PXT3003). The choice for this additional dose was limited by the baclofen dosage, that could not be increased above 6 mg given twice a day, in order to avoid known side effects with this drug particularly for chronic administration in active young people, and to preserve a good safety profile. As there is no approved treatment in CMT1A, there is no comparator to introduce, as usually done in Phase III trials. The 2 tested doses will be compared only to Placebo in a randomized double-blind design with 3 balanced groups (1:1:1).

Study objective(s)	
Primary objective:
 
To assess the efficacy of PXT3003 compared to Placebo on the disability measured by the ONLS score in CMT1A patients treated for 15 months.
 
Secondary objectives:
 
 - To assess the efficacy of PXT3003 compared to Placebo on clinical and functional tests, electrophysiological parameters, and measures of quality of life; - To assess the safety and tolerability of PXT3003 compared to Placebo; - To assess plasma concentrations of PXT3003 components (at peak and trough) when administered with 2 different doses; - To assess the change over time of potential blood biomarkers; - To assess molecular changes in skin biopsy, when this procedure will be possible (ancillary sub-study); - To explore potential new imaging biomarkers by leg MRI, when this procedure will be possible (ancillary sub-study).
Inclusion criteria	
 1. Male or female, aged from 16 to 65 years; 2. Patient with a proven genetic diagnosis of CMT1A; 3. Mild-to-moderate severity assessed by CMTNS-v2 with a score >2 and ≤18; 4. Muscle weakness in at least foot dorsiflexion (clinical assessment); 5. Motor nerve conduction of the ulnar nerve of at least 15m/sec; 6. Providing signed written informed consent to participate in the study and willing and able to comply with all study procedures and scheduled visits.
Exclusion criteria	
 1. Any other associated cause of peripheral neuropathy such as diabetes; 2. Patients with another significant neurological disease or a concomitant major systemic disease; 3. Clinically significant history of unstable medical illness since the last 30 days (unstable angina, cancer...) that may jeopardize the participation in the study; 4. Significant hematologic disease, hepatitis or liver failure, renal failure; 5. Limb surgery within six months before randomization or planned before trial completion; 6. Clinically significant abnormalities on the pre-study laboratory evaluation, physical evaluation, electrocardiogram (ECG); 7. Elevated ASAT/ALAT (> 3 x ULN) and elevated serum creatinine levels (> 1.25 x ULN); 8. History of recent alcohol or drug abuse or non-adherence with treatment or other

[figure not shown]
Exclusion criteria (con't)	
experimental protocols;
 
9. Patients using unauthorized concomitant treatments including but not limited to baclofen, naltrexone, sorbitol (pharmaceutical form), opioids, levothyroxin and potentially neurotoxic drugs such as amiodarone, chloroquine, cancer drugs susceptible to induce a peripheral neuropathy; (list provided in appendix 1). Patients who can/agree to stop these medications 4 weeks before randomization and during the whole study duration can be included;
 
10. Female of childbearing potential (apart of patients using adequate contraceptive measures), pregnant or breast feeding;
 
11. Known hypersensitivity to any of the individual components of PXT3003;
 
12. Porphyria as it is a contra indication to baclofen, and it may also induce neuropathy;
 
13. Suspected inability to complete the study follow-up (foreign workers, transient visitors, tourists or any others for whom follow-up evaluation is not assured);
 
14. Limited mental capacity or psychiatric disease rendering the subject unable to provide written informed consent or comply with evaluation procedures;
 
15. Patients who have participated in another trial of investigational drug(s) within the past 30 days;
 
16. If a patient from the same family, living in the same household, has already been included in this study, it will not be possible to include another patient from the same family to avoid mixing of therapeutic units; therefore there would be a risk of inversion of the blind treatments which could jeopardize the interpretation of study results.

Investigational treatments	
PXT3003 is a fixed dose combination of RS-baclofen, naltrexone hydrochloride and D-sorbitol. Two doses of PXT3003 will be tested:
 
Dose 1 = 3 mg baclofen, 0.35 mg naltrexone and 105 mg sorbitol given twice daily;
 
Dose 2 = 6 mg baclofen, 0.70 mg naltrexone and 210 mg sorbitol given twice daily;
 
The control group will be matching placebo.
 
Patients will be randomized in 3 groups in order to receive either PXT3003 at one of the 2 different doses or placebo.
 
PXT3003 and placebo will be supplied as 100 mL clear oral solution in amber glass bottle (for 10 days of treatment) which will be delivered with a plastic adapter and an adaptable plastic pipette for medication dispensation which will be graduated with a 5 ml graduation corresponding to the full dose and 2.5 mL for the half-dose of medication to be administered. Each strength of PXT3003 corresponding to one of the tested dose levels and the placebo will have the same presentation and taste.
 
PXT3003 and placebo will be provided in carton boxes of 4 bottles.
 
The study drug (PXT3003 or matching placebo) will be administered per oral route 5 ml twice daily (morning and evening with food) for 15 months.
 
To improve tolerability, treatment should start progressively (for all randomized patients): half dose (2.5 mL of the liquid formulation) will be administered twice a day during the two first weeks and then will be increased to the full dose (5 mL of the liquid formulation) twice a day until the end of study treatment.

Concomitant treatments	
Authorized treatments:
 
Standard care for CMT1A, particularly occupational and physical therapy or drugs for pain (excluding opioids and benzodiazepines) are authorized and should be reported in the CRF;
 
Prohibited treatments:
 
 - High doses of Ascorbic acid (\geq1 g/day) - Levothyroxine;

Concomitant treatments (con't)	
 - Baclofen, naltrexone, and sorbitol in their current pharmaceutical forms at full dose. The use of opiates, and potentially neurotoxic drugs should also be avoided. 
A list of non-recommended treatments is provided in protocol section 21.

Primary efficacy endpoint	Improvement of disability measured by the Overall Neuropathy Limitation Scale (ONLS) score.
Secondary efficacy endpoints	
 - Responders Rate to PXT3003 therapy defined as a patients improving on ONLS at end of treatment; - The effect of the studied PXT3003 dosages on the following endpoints: 
 ▪ Arm and leg sub-items of ONLS; ▪ Charcot-Marie-Tooth Neuropathy Score version 2 (CMTNS-v2), including its sub-items; ▪ Nine-hole Peg Test (9-HPT) performed on non-dominant hand; ▪ Quantified Muscular Testing (QMT) by Hand grip and Foot dorsiflexion dynamometry (mean of both sides); ▪ Time to walk 10 meters; ▪ Electrophysiological parameters assessing sensory and motor responses of ulnar and radial nerves (non-dominant side) including: 
 ○ Compound Muscle Action Potential (CMAP) on ulnar nerve; ○ Sensory Nerve Action Potential (SNAP) on radial nerve; ○ Nerve conduction velocity (NCV); ▪ Quality of life measured by: 
 ○ EuroQol 5-Dimensional Health-related Quality of Life scale (EQ-5D); ○ VAS on self-assessment of the individualized main impairment in daily activities defined at baseline with the patient.
Secondary safety endpoints	
Safety and tolerability of PXT3003 will be compared to placebo on the following parameters:
 
 - Incidence of all Treatment Emergent Adverse Events (TEAEs); they will be evaluated by type/nature, severity/intensity, seriousness, duration, relationship to study drug, and outcome; - Incidence of related TEAEs (including possibly and probably related TEAEs) with a moderate or severe intensity; - Incidence of AE leading to withdrawal of study drug; - Incidence of Serious Adverse Events (SAEs); - Change in physical examination, vital signs (blood pressure and heart rate), 12-lead ECG, and laboratory data (hematology and blood chemistry).
Additional exploratory endpoints	
 ▪ Plasma concentrations of baclofen, naltrexone and 6β-naltrexol will be obtained at Baseline, 6-months, 12-month and 15-month visits (PK samples at trough and at peak). ▪ Blood biomarkers: blood sampling will be performed for biomarkers and the tubes will be stored at -80°C 
 ○ Pharnext has identified potential blood biomarkers in the previous phase II that need to be confirmed in this phase III: tryptophan, alanine, serotonin, T4, free cholesterol. Other markers could be assessed for quantification studies, and thus identified later after the accomplishment of this clinical trial. ○ Gene expression studies (microarrays and PCRs) may be also performed aiming to identify genes that could change in response to PXT3003 treatment, which could confer them the property of pharmacodynamics candidates. ○ DNA sequencing to advance the understanding CMT1A disease for the research

Additional exploratory endpoints (con't)	
community in general for research purposes.
 
 ▪ Skin biopsy (optional ancillary sub-study) for molecular biology will be done (fixation for RNA preservation during 24 hours and then storage at -80°C until pick-up). Analysis RNA will be performed by Pharnext. ▪ MRI measure of muscle/fat index in the leg (optional ancillary sub-study), by MRI quantification of lower limb muscles and fatty muscle infiltration with centralized reading.
Statistical considerations	
Analysis populations: The Full Analysis Set (FAS) will be constituted by all the randomized patients. The Per-Protocol (PP) population will include all the patients of the FAS without major protocol violation during the course of the study.
 
All the efficacy analyses will be conducted on the FAS population and reproduced on the PP population for sensitivity purposes. The safety analyses will be conducted on the FAS, given that all randomized patients will receive at least one dose of treatment.
 
Primary efficacy analysis: The significance of the studied drug effect compared with Placebo will be tested by an Analysis of Covariance (ANCOVA) on the summary mean of ONLS at 12 and 15 months adjusted for baseline ONLS values. ANCOVA will be featured by a Linear Mixed Model (LMM), including baseline ONLS values and treatment as fixed factors, and center as random effect.
 
Two active doses will be compared to Placebo. As the monotonicity of dose effect is not assumed, each dose will be compared at a two-sided 2.5% significance level, in order to preserve an overall false-positive rate of 5%.
 
Sample size calculation: Assuming ANCOVA with 2 post-baseline measures, a linear correlation coefficient of ONLS of $R = 0.75$ between baseline and end of the study, a standard deviation of ONLS of $SD \cong 1$, a standardized mean difference of $SMD = 0.3$ should be detected versus Placebo with a power of 90% at a two-sided 2.5% significance level when the sample size reaches at least 89 patients per group. Assuming a drop-out rate of $\cong 10\%$, we anticipate recruiting 100 patients per group for a total of at least 300 patients.
 
Secondary efficacy analyses: The primary ANCOVA analysis based on the summary mean at 12 and 15 months will be repeated on the other quantitative efficacy endpoints (see above). The significance of the treatment effect on each quantitative endpoint will also be evaluated based on the difference compared to Placebo in change from baseline at each individual visit and in slope of progression over the duration of the study. The proportion of responders at 15 months will be assessed through a Generalized Linear Mixed Model (GLMM) featuring logistic regression, and admitting center as a random effect.
 
Missing data: Missing values will be imputed using a linear model estimated on the Placebo group. The potential impact of missing data on the study's conclusions will be evaluated.
 
Safety analyses: Safety and tolerability will be assessed by summarizing and analyzing adverse events (AEs), change in physical examination, vital signs, electrocardiogram (ECG) and laboratory data.
 
Data Safety Monitoring Board (DSMB): An independent DSMB will regularly follow the progress of the clinical trial, monitor safety data and critical efficacy variables, and be consulted concerning the opportunity of modifying the sample size or terminate the trial for futility.
 
Adaptive sample size: An estimation of the adjusted standard deviation (ASD) will be performed when 80 patients are available. In case where the absolute value of the difference between the observed ASD and the value used for initial sample size calculation


Statistical considerations (con't)	
exceeds 0.1, the sample size will be recalculated. The adaptive sample size calculation will be organized blind to treatment and do not require any type-I adjustment.
 
Futility analysis: A one-stage Futility stopping will be based on Conditional Power, probability to detect a significant result at the end of the study, given the results observed at an intermediate time. Conditional Power (CP) will be estimated through B-values and (Lan and Wittes, 1988; Lan and Zucker, 1993). This analysis will be carried out by a third party statistician when at least 100 patients are available, and futility threshold will be $CP_{min}=0.10$ involving a slight increase of type 2 error ($\beta = 0.1/0.9 = 0.111-0.10 \cong 0.01$) (Proschan, 1999). This intermediate futility analysis does not require any type-I adjustment, this trial does not plan g rejection of the null hypothesis before its end.
 
Further details will be described in the Statistical Analysis Plan (SAP) as appropriate.

Study schedule	
Usually patients come to visit their specialist annually and many of them may live far from the reference center, so the number of visits is limited.
 
The study will be conducted for a total of 15 months with evaluation visits at baseline (screening and/or randomization visit), at 6, 12 and 15 months.
 
Intermediate visits are scheduled at 3 and 9 months for drug dispensation, checking safety (AEs) and treatment compliance. Eventually if local regulations allow that the dispensing of medication can be organized by shipping, these intermediate visits at 3 and 9 months may be made by phone call.
 
Visits will be scheduled as following:
 
 ▪ V0 - Screening visit: Day-1 to Day -30 max ▪ V1 - Inclusion visit (Baseline): at Day 0 ▪ V2 - 3-month visit (or telephone call): at Day 90 ± 8 Days ▪ V3 - 6-month visit: at Day 180 ± 10 Days ▪ V4 - 9-month visit (or telephone Call): at Day 270 ± 10 Days ▪ V5 - 12-month visit: at Day 360 ± 10 Days ▪ V6 - 15-month visit: at Day 450 ± 10 Days 
If one visit date is changed (anticipated or delayed), the next visit should occur according to the original schedule

Extension study, a DB 9-month Follow-up	
In order to stimulate the recruitment and motivate patients to be enrolled, patients having completed the 15-month study will be eligible to receive PXT3003 in a follow-up extension trial for 9 months if they are willing to continue the treatment. They will be attributed to active drug by a second randomization. This 9-month extension study will provide additional long-term data on safety and additional efficacy data that could provide some evidence of disease modifying effect.

Planned dates	
 - CTA & IND submission: from June 2015 - Start (First patient in): Q4 2015 - Patients recruitment: 1 year (end of recruitment: Q4 2016) - Study duration for each patient: 15-month double-blind period - Last patient out (ie., end of study): expected Q1 2018 in all the countries, except in Germany where the LPO is expected Q3 2018* - Clinical Study Report: expected Q2 2019 
* due to longer interruption of the study in Germany regarding the occurrence of crystals in the dose 2 IMP, the LPO in Germany is expected in Q3 2018

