14.2 Primary efficacy analysis

The significance of the studied drug effect compared with Placebo will be tested by an Analysis of Covariance (ANCOVA) on the summary mean of ONLS at 12 and 15 months adjusted for baseline ONLS values. ANCOVA will be featured by a Linear Mixed Model (LMM), including baseline ONLS values and treatment as fixed factors, and center as random effect. The use of two repeated post-baseline measures increases the power to detect treatment differences in mean levels of the outcome measure over time (Frison and Pocock, 1992; Morgan and Case, 2013).

Two active doses will be compared to Placebo. As the monotonicity of dose effect is not assumed, each dose will be compared at a two-sided 2.5% significance level, in order to preserve an overall false-positive rate of 5%.

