14.3 Sample size calculation

Assuming ANCOVA with 2 post-baseline measures, a linear correlation coefficient of ONLS of $R = 0.75$ between baseline and end of the study, a standard deviation of ONLS of $SD \approx 1$, and a negligible between center standard deviation (estimated $SD = 0.13$ [0;0.35]), the resulting adjusted standard deviation $ASD \approx [1*(1-.75^2)]^{.5} \approx 0.65$, thus a minimum clinically relevant difference in ONLS should be a Cohen's Δ of $0.65/2 \approx 0.325$, rounded to $\Delta = 0.3$. From calculations based on compound symmetry of the covariance matrix (Frison and Pocock, 1992, Morgan and Case, 2013), such a difference should be detected versus Placebo with a power of 90% at a two-sided 2.5% significance level when the sample size reaches at least 89 patients per group. Assuming a drop-out rate of $\approx 10\%$, we anticipate recruiting 100 patients per group for a total of at least 300 patients.

The parameters needed for sample size calculation were evaluated based on historical trials (Micallef, Attarian *et al.*, 2009; Pareyson, Reilly *et al.*, 2011; Attarian, Vallat *et al.*, 2014).

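### After V1.4 stops Dose 2, the synopsis and section 14.3 still state 90% power versus Placebo without limiting it to Dose 1

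*Combined protocol and SAP*

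**What the plan says.** The synopsis (Total expected number of patients) justifies 100 patients per group as the number "to achieve a power of at least 90% to detect the expected effect as significant with the primary efficacy analysis". Section 14.3 gives the basis: with 89 patients per group, "such a difference should be detected versus Placebo with a power of 90% at a two-sided 2.5% significance level". It then allows about 10% drop-out to reach 100. The calculation assumes two post-baseline measures and "a linear correlation coefficient of ONLS of $R = 0.75$ between baseline and end of the study".

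Section 14.2 makes the primary variable the "summary mean of ONLS at 12 and 15 months adjusted for baseline ONLS values". It keeps both active doses as primary comparisons: "each dose will be compared at a two-sided 2.5% significance level".

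The V1.4 rationale at the front of the document says: "Hence, the use of PXT3003 dose 2 will be prematurely discontinued from the study". Dose 2 patients leave once their end-of-study assessments are done. The only statistical instruction, in the amendment's impact table, sends the incomplete Dose 2 data to section 14.5. That section imputes missing values from a linear model fitted to Placebo. It moves an early-interruption visit to the next regular visit if it falls inside a time frame, and otherwise leaves it out of inferential analyses. Neither the model's predictors nor the time frame is specified. No revised power is given.

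**The concern.** The 90% was computed for groups in which about nine patients in ten supply ONLS at both 12 and 15 months. V1.4 cuts follow-up in one of the three groups, so the premise no longer holds for Dose 2. The text does not say so, although V1.4 edited other parts of the synopsis, such as the planned dates.

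The risk lies in interpretation. Section 7 describes Dose 2 as the dose expected to be more active. A non-significant Dose 2 result set beside an unqualified 90% could be taken as good evidence against an effect, when part of the explanation may be lost visits and values imputed towards Placebo.

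**Working it through.** **Inputs.** From section 14.3: difference 0.3 ONLS points, SD 1, R = 0.75 under compound symmetry, two post-baseline measures, two-sided 2.5%, 10% drop-out. From the synopsis: 100 per group, first patient in Q4 2015, one year of recruitment ending Q4 2016, visits at days 360 and 450 (each ±10). From V1.4: decision date 18 September 2017. Not given, so assumed: uniform entry, the section 14.5 predictors, the section 14.5 time frame, and the length of the recall.

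**1. The plan's own figure reproduces.**
- Variance of the two-visit mean given baseline: SD² × [(1 + R)/2 − R²] = 0.875 − 0.5625 = 0.3125, so the adjusted SD is 0.559.
- Normal approximation: n = 2 × (2.241 + 1.282)² × 0.3125 / 0.3² = 86.2, so 87 per group. With the noncentral t, 88 gives 90.2% and 89 gives 90.5%.
- Drop-out: 89 / 0.9 = 98.9, so 99, stated as 100.
- With one visit the variance is 1 − 0.5625 = 0.4375 and n is 121. The 89 therefore depends on having both visits.

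**2. Visits lost at a cut-off of 18 September 2017.** Month 12 needs entry by 23 September 2016 (360 days earlier). Month 15 needs entry by 25 June 2016 (450 days earlier).

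| Entry (uniform) | Month 12 observed | Month 15 observed |
|---|---|---|
| 1 Oct 2015 - 30 Sep 2016 | 98% | 73% |
| 15 Nov 2015 - 15 Nov 2016 | 86% | 61% |
| 1 Jan - 31 Dec 2016 | 73% | 48% |

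The recall alone therefore removes 2-27% of month-12 and 27-52% of month-15 visits. The first calendar ends in Q3 2016, earlier than the synopsis plans. Last patient out in Q1 2018 (outside Germany) minus 450 days points to last entry between 8 October 2016 and 5 January 2017, though study interruptions could also have moved that date.

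**3. Why power falls.** Fewer values are observed, and a Placebo model using baseline alone gives a missing Dose 2 value no treatment effect. For January-December entry the observed share averages (0.73 + 0.48)/2 = 0.605. After 10% drop-out it is 0.545, so the expected difference is 0.3 × 0.545 = 0.16. Imputed values also vary less, which changes the standard error, so power was simulated.

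**4. Power with the cut-off at 18 September 2017.** ANCOVA on the two-visit mean, 100 per arm, 10% drop-out, 4,000 runs per cell. Columns show the predictors in the Placebo imputation model.

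| Entry | Baseline only | Baseline and month 12 | Baseline, months 6 and 12 |
|---|---|---|---|
| No stop | 90% | 91% | 93% |
| Oct 2015 - Sep 2016 | 84% | 87% | 91% |
| Mid-Nov 2015 - mid-Nov 2016 | 75% | 78% | 89% |
| Jan - Dec 2016 | 59% | 64% | 86% |

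The last column assumes the full 0.3-point effect is already present at month 6. A smaller early effect would lower it. A separate simulation gave 58-90% overall, within about a point at each end, and that range is used below.

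**5. Power with the section 14.5 shift rule.** End-of-study visits are assumed to spread over 60 days, with a 10- to 45-day window for shifting (2,000 runs): 88-92% for October-September entry, 84-92% for mid-November, 72-90% for January-December. A separate simulation under the same two assumptions gave about 70-92% overall.

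**The case against.** The strongest reply is that nothing was miscalculated. The 90% is a prospective justification, it reproduces, and an unplanned supply failure does not make it wrong in retrospect. Precision for Dose 2 will show in its confidence interval. The amendment openly says that Dose 2 data are incomplete, and section 14.5 promises to evaluate the impact of missing data and to run sensitivity analyses. The group size is also a minimum, and section 14.8 allowed it to be revised. All of this is fair, and it limits the point to a statement left unqualified after an amendment. It does not remove it: the reader is still given one power figure for two primary comparisons, and it rests on follow-up that one of them no longer has.

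Three stronger readings are tempting and not supported.
- A reader might infer that Dose 2 would miss the planned effect about four times in ten. The 58% floor needs January-December 2016 entry, baseline-only imputation, and no use of end-of-study visits after the decision date. The documents fix none of these. Patients leave only after end-of-study assessments, which include ONLS (section 11.2.7), and section 14.5 admits those values within its time frame.
- A reader might infer that losses exceed the planned 10% at both visits. At month 12 the low end is 2%.
- A reader might take the synopsis sentence as an explicit promise for each dose. The per-dose reading comes from sections 14.2 and 14.3.

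**Conclusion.** The point holds as a correction to the stated power. After V1.4, the 90% is no longer supported for Dose 2 versus Placebo; Dose 1 keeps its planned power. Dose 2 power is about 58-90% if visits stop counting on 18 September 2017, and about 70-92% if end-of-study visits are shifted under section 14.5 with an assumed 60-day recall and 10- to 45-day window. Both ranges assume 100 per arm, uniform entry within the planned dates, 10% ordinary drop-out and Placebo-model imputation. A shortfall is likely if recruitment ended in Q4 2016. It is not certain, because both ranges reach 90%. Its size depends on the actual visit dates and the imputation predictors, which the documents do not give.

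**What to change.** In the synopsis and section 14.3:
- Limit the 90% statement to Dose 1 versus Placebo.
- State Dose 2 power recomputed from the actual number of randomised Dose 2 patients whose month-12 and month-15 ONLS values enter the primary analysis. Count end-of-study visits shifted under section 14.5, and use the section 14.5 imputation. Counting only visits before 18 September 2017 would discard values that section 14.5 may admit, and could understate the power.
- Add that a non-significant Dose 2 result should be read from its confidence interval and not against 90% power.

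The recalculation requires the section 14.5 predictors and time frame to be written down. The cost is a few sentences and one calculation from visit dates, and the stated figure for Dose 2 will probably be less favourable. No extra patients are needed.
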